### 8.2.3 Data and Safety Monitoring Plan

Participants enrolled on this study will be monitored by the UAB Comprehensive Cancer Center’s Clinical Trials Monitoring Committee (CTMC). Adverse reactions observed during treatment will be closely monitored by the Clinical Trials Monitoring Committee (CTMC) on a monthly basis. The CTMC is responsible for data and safety monitoring of the trial and adherence to the DSMP, and is serving as the Central DSMB for this study. The independent Quality Assurance Committee (QAC) is responsible for oversight of the operation of CTMC, including adherence to the DSMP. Reports from the CTMC are reviewed monthly by the QAC.

## 9.0 STUDY PARAMETERS AND CALENDAR

These procedures are fully outlined in the study calendar and summarized below.

### 9.1 Screening visit

After informed consent is obtained, a screening visit will be scheduled. This visit will include a **history and physical, clinical breast exam, a complete blood count** (includes platelet count, but no differential necessary), **PT/PTT, metabolic panel** (includes electrolytes, creatinine, and liver function tests), and a **screening mammogram**.

For premenopausal patients, the screening mammogram should be performed between days 2 and 10 of their menstrual cycle (follicular phase). For premenopausal subjects who are unable to schedule a mammogram during the follicular phase of their menstrual cycle, the days since last menstrual period (LMP) will be recorded in the Breast Image Submission Form, and follow up mammograms will be scheduled on the same day of their cycle in which their screening mammogram was completed +/- 5 days. All mammograms must be performed on a digital mammography machine using large paddles. Images should be taken using on-site mammography equipment (rather than off-site facilities), and serial measurements should be taken from the same mammography unit whenever possible. Each view from each breast must be saved as a single electronic image in raw DICOM (Digital Imaging and Communications in Medicine) format as instructed in Section 11.1.1. A site radiologist will perform a clinical reading of the screening mammogram; including a density score per American College of Radiology (ACR) BIRADS guidelines (Figure 9). If a screening mammogram was performed within 120 days of study registration as part of the patient's routine clinical care, it can be estimated how many days into the menstrual cycle the patient was when it was performed (or the patient is postmenopausal), and it was obtained using a digital mammography unit, a digital copy of the original film will suffice, as long as that digital copy includes whole electronic images in raw DICOM format as outlined in Section 11.1.1. In that case, a copy of the radiology report should be retrieved at the same time as the digital mammogram. If both clinical reading and clinical density assessment were provided on that report, that will suffice. Otherwise, the outside film must be submitted for a reading by a site radiologist who will provide a reading and density assessment according to Figure 9 in Section 5.2. Detailed instructions on electronic submission of study mammograms are in Section 11.1.1.

For subjects whose menopausal status is unclear based on clinical history alone (see definitions in inclusion criteria below), a **FSH** level will be drawn at the time of the screening visit. For subjects who are premenopausal and have not had a menstrual period within 28 days, a blood **beta-HCG** test will also be performed.

### 9.2 Other baseline study parameters

Screen-eligible patients will be scheduled for baseline **RPFNA** (for consenting patients at FNA-participating sites) between days 2 and 10 of their menstrual cycle (follicular phase) and phlebotomy for circulating biomarker assays (all sites) to be performed within 60 days of completion of the screening visit (for patients consented prior to protocol version 3/9/2015 and all previously consented patients as of 10/26/15). A *urine collection* and a *blood draw* after at least an 8 hour fast must also be scheduled within the same time window for **lipid profile, anti-thrombin III, bone turnover markers, and circulating**

**biomarkers** (including insulin growth factors, sex steroid hormones, CYP2D6 SNPs, and tamoxifen metabolites). Please refer to Sections 11.2 [RPFNA], 11.3 [blood] and 11.4 [urine] for details regarding specimen collection, processing, and transfer.

In addition, if the patient is followed with annual screening **breast MRI** as part of their standard of care (applies to patients who have survived at least 8 years beyond their chest radiation exposure; please refer to the COG cancer survivorship guidelines [www.survivorshipguidelines.org] for those diagnosed with CAYAC prior to age 21 or the NCCN guidelines [www.nccn.org] for those diagnosed after age 21), then the most recent pre-registration MRI must be obtained for submission with the baseline screening mammogram described above. Patient reported symptoms will be assessed via standardized **Symptom Log**.

For sites who prefer to combine screening and baseline enrollment visits, the screening blood collection must be performed after an 8 hour fast and include the additional tests outlined in this section. The tubes drawn for most of the baseline tests below may be held until screen eligibility is confirmed; however, the anti-thrombin III level must be processed right away. The baseline RPFNA (for FNA-participating sites, for patients consented prior to protocol version 3/9/2015 and all previously consented patients as of 10/26/15) can be tentatively scheduled to follow completion of all screening activities, including registration in the Interactive Web Response System (IWRS), as described in Section 13.0, and then cancelled if eligibility is not confirmed by normal breast exam, benign mammogram, breast density reading of 2-3, and lab tests within stated parameters (see Section 5.0), or postponed if more time is needed. Study drug must be available for the participant to take home with them on the day the last baseline activity is performed.

### 9.3 Treatment initiation

The study CRA or CRN will register subjects as outlined in Section 13.0. The CRA or CRN will perform the randomization using the Sharp Clinical Services IWRS according to specifications in Section 12.3. Upon completion of the randomization, the Sharp Clinical Services IWRS will assign kit numbers to be dispensed. Kit labels include instructions on how to properly store and take the capsules as well as a contact number should any concerns regarding either the study medication or procedures arise.

### 9.4 Follow-up visits

For patients who consented to the RPFNA procedure (prior to protocol version 3/9/2015 and all previously consented patients as of 10/26/15), the study CRA or CRN will follow up with a call after the first week on study (**Day 8**) to confirm that the baseline RPFNA was tolerated well. All patients will be called after the fourth week (**Day 28**) to confirm that the patient is tolerating the medication well. Patient reported symptoms will be assessed via standardized **Symptom Log** administered via phone interview.

The patient will be asked to return their pill kits on **Day 90** for a pill count (reported on the **Adherence Tracking Form**) and refill dispensal, and patient reported symptoms will be assessed via standardized **Symptom Log** administered via phone interview.

A return visit will be scheduled for **Day 180**, during which a clinical breast exam will be performed and reported on a **Clinical Breast Exam Form**. Patient reported symptoms will be assessed via standardized **Symptom Log** form administered via in-person

interview. Patient reported health status changes will be assessed using the **Health Assessment Form**. In addition, health-related quality of life (QOL) will be assessed using the patient self-administered **NSABP Quality of Life Form**. A medication refill will be dispensed at that time, and pill count will be reported on the **Adherence Tracking Form**.

A phone follow-up will be conducted 3 months later (**Day 270**), including pill kit collection for assessment of adherence via pill count pill count (reported on the **Adherence Tracking Form**) and another refill dispensal. Patient reported symptoms will be assessed via standardized **Symptom Log** administered via phone interview.

A return visit will be scheduled for **Day 365**, during which a clinical breast exam (reported on a **Clinical Breast Exam Form**), fasting blood draw and urine collection, and patient reported symptom assessment will be performed via in-person interview documented on the **Symptom Log** form. Patient reported health status changes will be assessed using the **Health Assessment Form**. In addition, the patient will be given the self-administered **NSABP Quality of Life Form** to fill out. All lab results will be reported using a **Lab Values Form**. A repeat mammogram using a digital mammography machine with large paddles recommended to be timed to the follicular phase of the menstrual cycle (Days 2-10) will also be performed. The patient will be encouraged to have their mammogram at the same facility that did the initial study mammogram. If indicated (per COG or NCCN follow-up guidelines), a screening breast MRI should also be performed. If done while on study, it is suggested to time it to the follicular phase of the menstrual cycle (Days 2-10). A medication refill will be dispensed at that time, and pill count will be reported on the **Adherence Tracking Form**.

A phone follow-up will be conducted 3 months later (**Day 455**), including pill kit collection for assessment of adherence, collection of patient reported symptoms via standardized **Symptom Log** administered via phone interview, and refill dispensal, with pill count reported on the **Adherence Tracking Form**.

Another in-person visit will be scheduled for **Day 540** for clinical breast exam (reported on a **Clinical Breast Exam Form**) and assessment of patient reported symptoms via **Symptom Log**. Patient reported health status changes will be assessed using the **Health Assessment Form**. In addition, the patient will be given the self-administered **NSABP Quality of Life Form** to fill out. The pill kit will be collected for assessment of adherence via pill count pill count, reported on the **Adherence Tracking Form**, and another refill will be dispensed.

This will be followed by a phone follow-up 3 months later (**Day 630**) for pill adherence (reported on the **Adherence Tracking Form**), patient reported symptom evaluation via **Symptom Log**, and the last refill dispensal.

The final study visit will be conducted on **Day 730**, during which a final history and physical (reported on the **General History and Physical Form**), fasting blood draw, and urine collection will be performed. For patients who completed a baseline RPFNA, a post-treatment RPFNA will also be performed. Adherence will be reported on the **Adherence Tracking Form**, and patient-reported symptoms will be assessed via **Symptom Log**. Patient reported health status changes will be assessed using the **Health Assessment Form**. All lab results will be reported using a **Lab Values Form**. A repeat mammogram using a digital mammography machine with large paddles and

timed to the follicular phase of the menstrual cycle (Days 2-10) will also be performed. The patient will be encouraged to have their mammogram at the same facility that did the initial study mammogram. If annual screening breast MRI is indicated (per COG or NCCN follow-up guidelines), a repeat breast MRI should also be performed. If done while on study, it is suggested to time it to the follicular phase of the menstrual cycle (Days 2-10). A final telephone follow-up will occur one week later (**Day 738**) to ensure that the post-treatment RPFNA was well tolerated (only for patients consenting to the RPFNA procedure before protocol version 3/9/2015 and all previously consented patients as of 10/26/15).

All forms are due within 28 days of each scheduled visit and should be entered on the study Electronic Data Capture (EDC) website. Please refer to the [Treatment Monitoring and Follow-up SOP](#) for detailed instructions.

#### 9.5 **Long-term Follow-up**

After trial completion, the patient should be referred back to their local long-term survivorship clinic for continued follow-up, with their first return visit scheduled one year after their Day 730 study visit. Their first return visit will represent a new baseline survivorship clinic visit, and all organ function baseline assessments included in the COG survivorship guidelines should be repeated. This includes a comprehensive metabolic panel, which is recommended to be performed at baseline and as needed. Because of the association between standard dose tamoxifen and hepatic disease, special attention should be paid to symptoms and signs of hepatic disease on all subsequent annual follow-up survivorship clinic visits.

To monitor for significant medical events, including second malignancies that may occur after the two-year intervention, sites will submit an [Annual Follow-Up Form](#) for up to 10 years post-study completion, including participants that complete the two-year intervention and those that withdrew prior to completion. Subjects who are lost to follow-up will be reported to the coordinating center using this form. New cancer and any inpatient or outpatient procedures potentially related to the study will be reported using the [Breast Event Form](#) and [Other Event Form](#).

## STUDY CALENDAR\*

Treatment plan:	Prior to Treatment		Days on Study Treatment										Off
	Screening	Baseline (Day 0)**	8	28	90	180	270	365	455	540	630	730	738
STUDIES													
Primary Cancer Treatment History	X												
General History and Physical	X											X	
Health Assessment						X		X		X		X	
Breast Evaluations													
Clinical Breast Exam	X					X		X		X		X	
Breast Imaging a	X							X				X	
Breast Tissue Sampling b		X										X	
Blood/Urine Tests													
CBC and Metabolic Panel c	X							X				X	
PT/PTT (pre-RPFNA)	X											X	
Beta-Human Chorionic Gonadotropin ( $\beta$ -HCG), if needed d	X												
FSH level, if needed e	X												
Blood for circulating biomarkers f		X						X				X	
Fasting lipid profile g		X						X				X	
Anti-thrombin-III h		X						X				X	
Blood and urine to assess bone turnover i		X						X				X	
Self-Administered Questionnaires													
Demographics and BC risk Form j	X												
Family History Form j	X												
NSABP Quality of Life Form j		X				X		X		X		X	
Treatment Management													
Study tablet dispensal k		X			X	X	X	X	X	X	X	X	
Study tablet collection m						X		X		X		X	
Symptom log j		X		X	X	X	X	X	X	X	X	X	
Adverse Event Collection Form j						X		X		X		X	
Follow up phone call l			X	X	X		X		X		X		X

a Annual mammograms will be required as standard of care follow-up for this patient population per COG cancer survivorship or NCCN guidelines. For patients who are at least 8 years beyond their RT exposure, annual screening breast MRIs are recommended. Both forms of breast imaging will be timed to the menstrual cycle and submitted electronically as described in section 11.1.1.

b Will be done via RPFNA described in section 11.2, for patients consented prior to protocol version 3/9/2015 and discontinued for all participants 10/26/15.

c Platelet count should be included in the CBC panel, differential is not needed. The metabolic panel should include liver function tests.

d Only if premenopausal with irregular menstrual cycles, to rule out pregnancy (see eligibility criteria).

e Only if status-post hysterectomy without bilateral salpingo-oophorectomy, or does not have regular periods and pregnancy has been ruled out, to determine menopausal status (see eligibility criteria).

f Insulin growth factor-1 (IGF-1) and insulin growth factor binding protein-3 (IGFBP-3) will be determined (assay methods described in Section 11.7). Future analyses of sex steroid hormone levels, CYP2D6 SNPs and tamoxifen metabolite levels are also planned.

g Lipid profile includes total cholesterol, LDL-cholesterol, HDL-cholesterol, and triglycerides, determined using standard clinical assays.

h Anti-thrombin III (AT-III) is a measure of clotting propensity (a lower level suggests higher risk of clotting).

i Submit for serum bone-specific alkaline phosphatase (BSAP) and urine N-telopeptide crosslinks (NTX), which measure bone formation and bone resorption, respectively.

j Included in the appendix.

k The initial Day 0 pill kit will be dispensed at the time of blood and/or tissue sampling. The Day 180, 365, and 540 refills will be dispensed at the time of their follow-up clinical breast exams. Study capsules may be dispensed without waiting for lab clearance.

l Follow up calls are to confirm the patient is tolerating the RPFNA and to determine adherence and arrange medication refill dispensal.

m Patients will return 2 study kits at the time of their visit

\* The protocol allows for a +/- 60 business day window for all in person visits and +/- 5 business days for scheduled phone visits.

\*\* The Day 0 visit (must be done within 60 days of completion of the screen visit if scheduled separately)

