**Objective safety measures:**

**Adverse events.** The number of grade 2-4 toxicities observed will be tabulated by treatment arm. Differences by treatment arm will be evaluated using Fisher exact tests.

**Biomarkers.** Total cholesterol, low and high density lipoprotein, triglycerides, anti-thrombin III enzymatic assay (for clotting propensity), and serum bone-specific alkaline phosphatase (BSAP, for bone formation) and urine N-telopeptides (NTX, for bone resorption) measurements will be treated as continuous variables. Transformed to normality as appropriate, the linear mixed effects model will be applied, using the unstructured mean model using and linear in time model, to assess the effects of low dose tamoxifen on these measurements over time.

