#### C. Molecular characteristics.

The following variables are known to influence efficacy of tamoxifen in the treatment of BC patients and will be analyzed at a later date.

*Endoxifen levels* – continuous, time-varying. These data will be available at t1 and t2.

*CYP variants* - dichotomous (yes/no), constant over the study period.

In addition to testing their significance as effect modifiers, we will also examine their relationship with the outcome variables (MBD, cytomorphology, proliferative index, etc) to validate known relationships. Proc Mixed for normal data and Proc GLMMIX for non-normal data in SAS 9.1 (Cary, North Carolina) will be used for analysis.

***Exploratory Aim 2: To examine the relationship between a low-dose tamoxifen regimen and clinical measures of efficacy and toxicity.***

For measures of clinical efficacy, we will document the occurrence of new breast cancer and DCIS diagnoses.

The assessment of clinical toxicity will include the following outcomes/measures:

- 1) incidence of uterine and other cancers during the study;
- 2) gynecological symptoms: any and the frequency of hot flashes, night sweats, vaginal discharge, vaginal bleeding or spotting, missed menstrual periods for pre-menopausal women, genital itching/irritation, and pain with intercourse, to be obtained from symptom log administered 10 times (baseline, days 28, 90, 180, 270, 365, 455, 540, 630, 730) ;
- 3) incident thromboembolic events (DVT, PE, TIA or stroke, and retinal vein thromboses);

4) incidence of cataract;

5) liver function abnormalities: total bilirubin, SGOT/AST, SGPT/ALT, measured at baseline, year 1, and year 2.

The *incidence* of new breast cancer, DCIS, non-breast malignancies, thromboembolic events, and cataract are expected to be low ( $\leq 5$  events per arm) during the study period given the sample size, based on statistics quoted in Investigational Brochure. Thus, we will initially compare the frequency of events by treatment group in a 2x2 table using the Fisher exact test, stratified on CYP2D6 status. We will also use poisson regression in cohort analysis to examine treatment differences in these outcomes adjusted for covariates, including CYP2D6.

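### No graded adverse-event form is scheduled before Day 180, at the drug-period phone contacts or at early exit, so capture of lesser events in women who quit early depends on unscheduled reporting

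*Combined protocol and SAP*

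**What the plan says.** **Schedule.** The Study Calendar (Section 9) has a row for the "Adverse Event Collection Form" with marks at Days 180, 365, 540 and 730 only. Its footnote on windows reads: "The protocol allows for a +/- 60 business day window for all in person visits and +/- 5 business days for scheduled phone visits".

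**Phone contacts.** During treatment there are calls at Days 28, 90, 270, 455 and 630; those at Days 8 and 738 serve the aspiration procedure only. Section 9.4 says the Day 28 call is "to confirm that the patient is tolerating the medication well". The calendar footnote on calls gives a more general purpose: "Follow up calls are to confirm the patient is tolerating the RPFNA and to determine adherence and arrange medication refill dispensal". The Symptom Log is completed at all five; Section 12.4, Exploratory Aim 2, describes it as "to be obtained from symptom log administered 10 times (baseline, days 28, 90, 180, 270, 365, 455, 540, 630, 730").

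**Event-driven reporting.** Section 8.0 uses the same form for all adverse events, and Section 6.3 requires them to be reported to the coordinating center. Serious events, and grade 3-4 toxicities of possible or greater attribution, go there within 24 hours of knowledge. Grade 2 toxicities of probable or greater attribution, menopausal-type symptoms excepted, go to the local investigator within 24 hours.

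**Exit.** The Study End Form (Section 14.3) records completion or withdrawal and, for voluntary withdrawals, whether side effects were the reason. No event term or grade is mentioned.

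**Analysis.** Section 12.4, Aim 2: "The number of grade 2-4 toxicities observed will be tabulated by treatment arm", with Fisher exact tests. No denominator is given and attribution does not restrict the count. Section 10.0 promises the toxicity outcome of every eligible subject.

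**The concern.** Safety and tolerability is a stated objective (1.2), and early intolerance is a large part of tolerability. A woman who stops in the first six months can leave without anyone having been scheduled to ask her about adverse events and grade them. The Symptom Log reaches her at Days 28 and 90, but the documents give no rule for turning an entry into a CTCAE grade with attribution.

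The 24-hour rules start when the site knows of an event; they do not prompt the question. They also do not reach grade 2 events of lower attribution, which the Aim 2 table nevertheless counts. If intolerance leads more women to quit on tamoxifen, more of that arm's events would go unrecorded and the difference between arms would look smaller than it is.

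**Working it through.** **Inputs.** 115 women per arm and 10% attrition a year (Section 12.5, Aim 1). Grade 2-4 rates of 0.5% on placebo and 9.1% on tamoxifen, 94 per arm at study end, Fisher's exact test, type I error 0.05, at least 80% power (Section 12.5, Aim 2).

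**1. The plan's own figure.** 115 × 0.9 × 0.9 = 93.15; rounding up at each year gives 94. Exact Fisher power at 94 per arm for 0.5% v 9.1%, by enumerating both binomials, is 85.7% one-sided and 75.4% two-sided; the two-sided pooled z approximation gives 79.2%. The stated 80% is met by a one-sided Fisher test. Sidedness is not stated for this comparison.

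**2. Women leaving before the first scheduled form.** With attrition even over time:
- Day 180: 1 − 0.9^(180/365) = 5.1%; 115 × 0.051 ≈ 6 per arm, about 12 in all.
- Late edge of the window: 60 business days are 12 weeks, or 84 calendar days, so the visit may fall anywhere from Day 96 to Day 264. 1 − 0.9^(264/365) = 7.3%; 115 × 0.073 ≈ 8 per arm.

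**3. The base for the loss.** The 94 per arm is already net of attrition. Women who left early are not among them, so their unrecorded events cannot lower the rate in those 94. The proper base is the 115 randomized. Expected tamoxifen-arm women with an event: 115 × 0.091 ≈ 10.5. On placebo it is 115 × 0.005 ≈ 0.6, so loss there matters little and is set to zero.

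**4. Power if a share L of tamoxifen-arm events is unrecorded.** Recorded rate = 9.1% × (1 − L); two-sided Fisher, 115 per arm.

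| L (assumed) | Events lost | Recorded rate | Power |
|---|---|---|---|
| 0 | 0 | 9.1% | 87% |
| 5% | 0.5 | 8.6% | 84% |
| 10% | 1.0 | 8.2% | 80% |
| 20% | 2.1 | 7.3% | 71% |
| 33% | 3.5 | 6.1% | 55% |

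**5. How plausible each loss is from early leavers alone.** About 5.8 tamoxifen-arm women leave before Day 180. If they have the average 9.1% rate and every event is missed, 5.8 × 0.091 ≈ 0.5 events are lost, the 5% row. The 10% row needs 1.05/5.8 ≈ 18% of them to have had an unrecorded grade 2-4 event, the 20% row 2.1/5.8 ≈ 36%, and the 33% row 3.5/5.8 ≈ 60%.

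**The case against.** The strongest reply is that the calendar is not the only route. Section 8.0 does not tie the form to calendar days, Section 6.3 requires reporting of known events, and Section 8.2.3 has adverse reactions monitored monthly. A woman stopped under the toxicity rules of 6.3 has, by definition, an event that the site already knows of, has graded and has attributed. Voluntary withdrawal is itself compared between arms, menopausal-type symptoms have their own longitudinal analysis, and the Annual Follow-Up Form covers women who withdrew. The form itself, in an appendix, and the Treatment Monitoring and Follow-up SOP were not available for this review and may ask for completion at exit.

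Most of this stands, and it rules out several stronger readings. A reader might infer that adverse events are gathered on four days only, or that women taken off drug for toxicity vanish from the table; Sections 6.3 and 8.0 say otherwise. One might treat all five calls as drug-tolerance checks, but only Day 28 is so described. One might take the 0-to-4 scale in Section 12.4 as the Symptom Log's scale, but that questionnaire is given at five six-monthly points, whereas the log is given ten times. And one might apply the loss to the 94 per arm, starting from 75% power; that counts attrition twice.

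What the reply does not cover is the event nobody asks about. The withdrawal comparison shows that women left, not what grade of event they had. The annual form looks for significant medical events. The promise in Section 10.0 to report toxicity for every eligible subject makes the missing exit assessment more noticeable, not less.

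**Conclusion.** The point holds as a limited gap in ascertainment. Before Day 180, between visits and at early exit, non-serious events, chiefly grade 2 of lower attribution, reach the Aim 2 table only if they are volunteered or noticed. About 6 women per arm are exposed to this before Day 180, or about 8 if the first visit falls at the late edge of its window.

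The direction is towards no difference if the loss is heavier on tamoxifen, which is plausible but not shown. The likely cost is modest: power falls from 87% to 84% if early leavers have average risk, and to 80% or 71% if 10% or 20% of tamoxifen-arm events are missed. These figures rest on the plan's event rates, even attrition, a two-sided test and an assumed loss; no document gives the share that would go unrecorded. The change is worth making because it is cheap, not because the safety comparison fails without it.

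**What to change.** - In the Study Calendar and Section 9.4, add the Adverse Event Collection Form, with CTCAE grade and attribution, to the existing Day 28, 90, 270, 455 and 630 contacts.
- In Section 14.3, require one with every Study End Form filed before Day 730.
- In Section 12.4, Aim 2, state that the comparison includes all women who started study drug, and give the sidedness of the Fisher test.

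The cost is a few extra minutes on calls already made and one more form at early exit. No new visit is needed.
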